7.2.5.1 Dose-Limiting Toxicity

A DLT is defined as a TEAE (using CTCAE V5.0) occurring during the first 28 days of dosing, as follows:

- Any death not clearly due to the underlying disease or extraneous causes
- Hematologic AEs:
 - Febrile neutropenia, defined as ANC $<1000 \text{ mm}^3$ with a single temperature of $\geq 38.3^\circ\text{C}$ or a sustained temperature of; $\geq 38^\circ\text{C}$ for more than 1 hour;
 - Neutropenia, Grade 4 that does not resolve to Grade 1 with granulocyte macrophage-colony-stimulating factor (CSF) or granulocyte-CSF treatment within 7 days;
 - Neutropenia or thrombocytopenia Grade 4 or higher present for >7 days, neutropenic infection, Grade 3;
 - Thrombocytopenia with clinically significant bleeding, Grade 3;
 - (Life-threatening) anemia, Grade 4.
- Non-hematologic AEs:
 - Any Grade ≥ 3 toxicities including maximally treated (with adequate antiemetic and other supportive care) Grade ≥ 3 nausea, vomiting, or diarrhea of >72 hours duration;
 - Grade ≥ 3 increased AST or ALT, or satisfying Hy's Law (i.e., $\text{AST}/\text{ALT} > 3 \times \text{ULN}$ with concomitant total bilirubin $> 2 \times \text{ULN}$ with no evidence of hemolysis and

alkaline phosphatase (ALP) $>2 \times$ ULN or not available), for patients with hepatic metastases: AST or ALT $>8 \times$ ULN or AST or ALT $>5 \times$ ULN for ≥ 14 days;

- Grade ≥ 3 non-hematologic laboratory abnormality requiring medical treatment or hospitalization, Grade ≥ 3 fatigue present for ≥ 1 week;
- Grade ≥ 3 electrolyte abnormality that lasts for >72 hours, unless the patient has clinical symptoms, in which case all Grade 3+ electrolyte abnormality regardless of duration counts as a DLT;
- Grade 4 laboratory abnormalities irrespective of duration;
- Grade 3+ irAEs except for those listed below.

In addition, any grade drug-related toxicity (with the exception of infusion-related reactions) which in the judgement of the Investigator or Sponsor requires removal of the patient from the study.

Patients who received $<80\%$ of both of the total intended Cycle 1 doses for reasons other than DLT will not be taken into account in the assessment of the overall DLT rate for the particular dose level cohort and can be replaced.

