Resumption of NM21-1480 administration for patients experiencing DLTs may be permitted according to the criteria described under Section “Dose Resumption”, if clinically appropriate, contingent on the return of the DLT to \leq Grade 0-1 severity or to baseline, and interruption or delay of treatment for no more than 35 days (i.e., 2 missed doses + 7 days) from the scheduled dosing and upon discussion with and approval by the Medical Monitor.

The following events shall not be regarded as a DLT:

- Grade 3 AE of tumor flare (defined as local pain, irritation, or rash localized at sites of known or suspected tumor) present for less than 7 continuous days
- Grade 3 Infusion-related reaction resolving within 6 hours and controlled with medical management
- Transient (≤ 6 hours) Grade 3 influenza-like symptoms or pyrexia controlled with medical management
- Grade 3 local reaction or headache that resolves to a maximal severity of Grade 1 within 24 hours
- Grade 3 skin toxicity, or increase liver enzyme (AST, ALT) that resolves to a maximum severity of Grade 1 within 7 days after initiation of medical management (e.g., immunosuppressant treatment)
- Grade 3 skin toxicity that improves to Grade 0 to 2 within 3 days

- Grade 3+ amylase or lipase elevation not associated with symptoms or clinical manifestations of pancreatitis does not represent a DLT
- Grade 3 treatment-related endocrinopathy AEs, such as adrenal insufficiency, adrenocorticotropic hormone (ACTH) deficiency, hyper- or hypothyroidism, or glucose intolerance, which resolve or are adequately controlled with physiologic hormone replacement (corticosteroids, thyroid hormones) or glucose-controlling agents, respectively
- Grade 3 laboratory abnormalities that improve to \leq Grade 2 within 3 days only if asymptomatic and if medical intervention was not required

Elevations of ALT/AST that are >3 -fold above baseline are to be considered adverse events of special interest (AESI) and to be reported with SAE timelines. The details on how to handle this situation are described in [Appendix VI](#), Section “Hepatitis”. In case of Grade 3+ hepatotoxicity, an initial ultrasound or image needs to be done to visualize the biliary tree and to rule out disease progression or occurrence of gall stones.

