- Is an important medical event. Important medical events that may not result in death, be life-threatening or require hospitalization may be considered a serious adverse drug experience, when based on appropriate medical judgement, they may jeopardize the participant or the participant may require medical or surgical intervention to prevent one of the outcomes listed in this definition. Examples of such events include invasive or malignant cancers, intensive treatment in an emergency room or at home for allergic bronchospasm, blood dyscrasias or convulsions that do not result in hospitalization, or development of drug dependency or drug abuse. Patients will be required to permanently discontinue NM21-1480 for the following TRAEs:
 - Any Grade 2 TRAE uveitis, eye pain or blurred vision that does not respond to topical therapy and does not improve to Grade 1 severity within the re-treatment period OR requires systemic treatment.
 - Any Grade 3 non-skin, TRAE lasting >7 days, with the following exceptions:
 1. Grade 3 TRAE uveitis, pneumonitis, bronchospasm, hypersensitivity reaction, or infusion reaction of any duration requires discontinuation.
 2. Grade 3 TRAE endocrinopathies adequately controlled with only physiologic hormone replacement do not require discontinuation.
 3. Grade 3 TRAE laboratory abnormalities not requiring medical treatment or hospitalization do not require treatment discontinuation except:
 - a. Grade 3 TRAE thrombocytopenia >7 days or associated with clinically significant bleeding requires discontinuation.
 - b. Any TRAE liver function test abnormality that meets the following criteria requires discontinuation:
 - i. AST or ALT >5-10 × ULN for >2 weeks or AST or ALT >10 × ULN.

- ii. Total bilirubin $>5 \times$ ULN.
- iii. Concurrent AST or ALT $>3 \times$ ULN and total bilirubin $>2 \times$ ULN without initial finding of cholestasis (elevation of alkaline phosphatase [ALP]).
- iv. For patients with hepatic metastases: AST or ALT $>8 \times$ ULN or AST or ALT $>5 \times$ ULN for ≥ 14 days.
- Any patient experiencing a Grade 4 toxicity or laboratory abnormality must be permanently discontinued.
- Any event that leads to delay in dosing lasting >35 days (i.e., 2 missed doses + 7 days in settings with intended biweekly dosing events) or >49 days (i.e., 2 missed doses + 7 days in settings with intended dosing events every three weeks) from the scheduled dosing requires discontinuation, with the following exceptions:

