9.2.7.1 Potential Hy's Law and Hy's Law

Cases where a patient shows elevations in liver biochemistry may require further evaluation and occurrences of AST or ALT $\geq 3 \times$ ULN together with total bilirubin $\geq 2 \times$ ULN without evidence of intra- or extra-hepatic bilirubin obstruction (elevated at least ALP) or Gilbert's syndrome will need to be reported as SAEs. Please refer to [Appendix II, Section 18.2](#) for further instruction on cases of increases in liver biochemistry and evaluation of Hy's Law.

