18.2 Appendix II: Liver Safety Monitoring and Assessment

Introduction

The purpose of this appendix is to provide guidance for the monitoring of drug-induced liver injury (DILI) during the course of the study. It should be noted that this section does not specify the end of study analyses of liver enzymes. The end of study liver enzymes analyses will be described in the SAP. Any patient enrolled in a study with active drug therapy and who reveals an increase of serum aminotransferases (AT) to $>3 \times$ ULN (to $>5 \times$ ULN in patients with liver metastases) or total bilirubin level (TBL) $>2 \times$ ULN should undergo detailed testing for liver enzymes (including at least ALP, ALT, AST and TBL). Testing should be repeated within 72 hours of notification of the test results. Patients should be asked if they have any symptoms.

Definition of Liver Abnormalities

Confirmed abnormalities will be characterized as moderate and severe where ULN is as shown in below table:

	ALT or AST		Total Bilirubin
Moderate	$>3 \times$ ULN (in patients without liver metastases), $>5 \times$ ULN (in patients with liver metastases)	or	$>2 \times$ ULN
Severe	$>3 \times$ ULN	and*	$>2 \times$ ULN

Abbreviations: ALT=alanine aminotransferase; AST=aspartate aminotransferase; ULN=upper limit of normal

*Samples taken simultaneously or within a maximum of 24 hours.

In addition, the patient should be considered to have severe hepatic abnormalities for any of the following:

- AST or ALT $>5-10 \times$ ULN for >2 weeks or AST or ALT $>10 \times$ ULN
- Total bilirubin $>5 \times$ ULN
- Concurrent AST or ALT $>3 \times$ ULN and total bilirubin $>2 \times$ ULN without initial finding of cholestasis (elevation of ALP)
- For patients with hepatic metastases: AST or ALT $>8 \times$ ULN or AST or ALT $>5 \times$ ULN for ≥ 14 daysThe Investigator may determine that abnormal liver function results, other than those described above, may qualify as moderate or severe abnormalities and require additional monitoring and follow-up

Follow-up Procedures

Confirmed moderate and severe abnormalities in hepatic functions should be thoroughly characterized by obtaining appropriate expert consultations, detailed pertinent history, physical examination and clinical laboratory tests. The study site personnel are to complete the eCRF. Patients with confirmed abnormal liver function tests (LFT) should be followed as described below:

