In the absence of an explanation for increased LFTs, such as viral hepatitis, pre-existing or acute liver disease, presence of liver metastases, or exposure to other agents associated with liver injury, the patient may be discontinued from study treatment. The Investigator may determine that it is not in the patient's best interest to continue study treatment. Discontinuation of study treatment should be considered if:

- AST or ALT $>5-10 \times$ ULN for >2 weeks or AST or ALT $>10 \times$ ULN
- Total bilirubin $>5 \times$ ULN
- Concurrent AST or ALT $>3 \times$ ULN and total bilirubin $>2 \times$ ULN without initial finding of cholestasis (elevation of ALP)
- For patients with hepatic metastases: AST or ALT $>8 \times$ ULN or AST or ALT $>5 \times$ ULN for ≥ 14 days

* Samples taken simultaneously or within a maximum of 24 hours.

In addition, if close monitoring for a patient with moderate or severe hepatic laboratory tests is not possible, study treatment should be discontinued.

Hy's Law Definition

1. Evidence that a drug can cause hepatocellular-type injury, generally shown by a higher rate than control of people with $3 \times$ AT elevations over the ULN ($2 \times$ elevations are too common in treated and untreated patients to be discriminating).
2. Cases of increased bilirubin (to at least $2 \times$ ULN) in people with concomitant AT elevation to at least $3 \times$ ULN (but it is almost invariably higher) and no evidence of intra- or extra-hepatic bilirubin obstruction (elevated ALP) or Gilbert's syndrome [Reference: Temple R. Hy's Law: Predicting Serious Hepatotoxicity. *Pharmacoepidemiol Drug Saf*.2006; 15(4):241-3].

FDA Guidance for Industry titled "DILI: Premarketing Clinical Evaluation" issued by the FDA on July 2009.

FDA Guidance for Industry:

1. The drug causes hepatocellular injury, generally shown by a higher incidence of 3-fold or greater elevations above the ULN of ALT or AST than the (nonhepatotoxic) control drug or placebo.
2. Among patients showing such AT elevations, often with AT levels much greater than $3 \times$ ULN, 1 or more also show elevation of serum TBL to $>2 \times$ ULN, without initial findings of cholestasis (elevated serum ALP).

3. No other reason can be found to explain the combination of increased AT and TBL, such as viral Hepatitis A, B or C; pre-existing or acute liver disease; or another drug capable of causing the observed injury.

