3.6.1 Dose-Limiting Toxicities (DLTs)

For Parts A, A-2, and B, DLTs are defined in section 7.2.5.1 of the protocol. DLT's will be identified by the investigator and recorded in the eCRF. The number of patients with DLTs will be summarized, and all DLTs will be listed by patient.

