3.6.3 Clinical Laboratory Tests

The number and percentage of patients with the following abnormalities will be presented:

- ALT $\geq 3 \times \text{ULN}$, $\geq 5 \times \text{ULN}$, $\geq 10 \times \text{ULN}$, and $\geq 20 \times \text{ULN}$
- AST $\geq 3 \times \text{ULN}$, $\geq 5 \times \text{ULN}$, $\geq 10 \times \text{ULN}$, and $\geq 20 \times \text{ULN}$
- Total bilirubin $\geq 2 \times \text{ULN}$
- Potential Hy's Law cases: ALT or AST $> 3 \times \text{ULN}$, total bilirubin $\geq 2 \times \text{ULN}$, and ALP $< 2 \times \text{ULN}$ at the same visit

Selected clinical laboratory evaluations (i.e., chemistry and hematology) may be summarized using descriptive statistics or CTCAE grade shift tables as appropriate.

All local laboratory assessments, including chemistry, coagulation, hematology, thyroid function will be listed by patient. Applicable chemistry (Alanine Aminotransferase, Albumin, Alkaline Phosphatase, Amylase, Aspartate Aminotransferase, Bilirubin, Creatinine, Glucose, Lactate Dehydrogenase, Lipase, Potassium, Sodium), and hematology (Eosinophils, Hemoglobin, Leukocytes, Lymphocytes, Neutrophils, Platelets) parameters will be graded according CTCAE v5.0. For some laboratory tests, the CTCAE criteria may include qualifying definitions (e.g., clinical AE and/or requirement for concomitant medication) in addition to the specific laboratory value used for the definition of the toxicity grades. For such tests, the qualifying definitions will not be used for the assignment of toxicity grades.

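### Read as written, the Hy's Law arm of the DLT definition requires raised (or missing) ALP, the reverse of the SAP and of the protocol's own liver sections

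*Protocol*

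**What the plan says.** The hepatic bullet of protocol 7.2.5.1 gives two routes to a DLT: Grade 3 or higher AST/ALT, or meeting Hy's Law. The second is spelled out as AST/ALT above 3 × ULN together with total bilirubin above 2 × ULN, no sign of hemolysis, and "alkaline phosphatase (ALP) $>2 \times$ ULN or not available".

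Every other statement on the subject points the other way on ALP:

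- SAP 3.6.3, potential Hy's Law cases: "and ALP $< 2 \times \text{ULN}$ at the same visit".
- Protocol 9.2.7.1: "without evidence of intra- or extra-hepatic bilirubin obstruction (elevated at least ALP").
- Protocol 9.2.1.4, permanent discontinuation: "without initial finding of cholestasis (elevation of alkaline phosphatase [ALP").
- Appendix II, severe hepatic abnormality and discontinuation: "without initial finding of cholestasis (elevation of ALP").
- Appendix II, Hy's Law definition: "no evidence of intra- or extra-hepatic bilirubin obstruction (elevated ALP").

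SAP 3.6.1 adds no definition of its own: "DLTs are defined in section 7.2.5.1 of the protocol".

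**The concern.** Hy's Law, as the protocol itself describes it, concerns hepatocellular injury: raised aminotransferases and bilirubin that cholestasis does not explain. The ALP condition is there to exclude cholestasis. With the sign as printed, it selects for it.

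DLT incidence is a primary endpoint of Part A and drives the BOIN dose decisions. The same definition serves Part A-2 and Part B. Hepatitis is the toxicity that the protocol's background section describes for an earlier 4-1BB agonist, so this arm covers an event of particular interest. DLTs are identified by the investigator and confirmed by the SMC. The error therefore affects what those people are told to count, not a programmed laboratory table. The final report could also list a potential Hy's Law case under SAP 3.6.3 that the Hy's Law arm of the DLT definition excludes.

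**Working it through.** **Step 1: classify one case under each text.** Take a patient with AST/ALT above 3 × ULN, bilirubin above 2 × ULN and no hemolysis, and vary only ALP.

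| ALP | 7.2.5.1, literal | 7.2.5.1, if the negation also covers ALP | SAP 3.6.3 |
|---|---|---|---|
| above 2 × ULN | meets the arm | does not | not a case |
| below 2 × ULN | does not | meets the arm | case |
| not measured | meets the arm | unclear | not counted as written |

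On the literal reading, 7.2.5.1 and SAP 3.6.3 classify every measured ALP above or below 2 × ULN in opposite ways. The protocol's liver sections speak of raised ALP without a 2 × ULN cut-off, so the conflict with them is one of direction, not of threshold.

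**Step 2: test the other reading.** If the negation before hemolysis also governs ALP, the direction agrees with the SAP. The closing words about unavailable ALP then fit poorly, because the sentence would require no evidence of ALP being unavailable. Those words work naturally after a condition of ALP below 2 × ULN, where they mean that the case counts unless cholestasis is shown.

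**Step 3: find the cases affected.** Grade 3 or higher AST/ALT and other Grade 3 or higher non-hematologic toxicity are already DLTs. The arm decides the matter only when:

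- AST/ALT and bilirubin exceed 3 × and 2 × ULN but both stay below Grade 3; or
- Grade 3 AST/ALT is exempted under the list in 7.2.5.1 of events not regarded as DLTs, which includes "increase liver enzyme (AST, ALT) that resolves to a maximum severity of Grade 1 within 7 days" of starting medical management.

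**Step 4: what one extra DLT could do.** Inputs are the final counts in Table 10-5 and the rules in Table 10-2: escalate at a DLT rate of 0.236 or less, de-escalate at 0.359 or more. The added case is hypothetical.

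| Dose | Observed | With one more DLT | BOIN action |
|---|---|---|---|
| 80 mg | 1/5 = 0.20 | 2/5 = 0.40 | escalate → de-escalate |
| 240 mg | 0/3 = 0 | 1/3 = 0.33 | escalate → stay |
| 800 mg | 0/9 = 0 | 1/9 = 0.11 | escalate, unchanged |
| 1400 mg (Part A-2) | assumed 0/5 | 1/5 = 0.20 | escalate, unchanged |

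The Part A-2 row uses the 5 patients enrolled (SAP section 6) and assumes that all were evaluable with no other DLT.

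**Step 5: patients to check.** 26 exposed in Part A (protocol 5.3.2), plus 5 in A-2, 5 in B1, 5 in B7 and 10 in B8 (SAP section 6): 26 + 5 + 5 + 5 + 10 = 51. This is an upper limit, since it assumes every enrolled patient was dosed.

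**The case against.** The best defence is that the clause only explains a term defined elsewhere. Sections 9.2.7.1 and Appendix II exclude raised ALP, a clinician would carry the negation across to ALP, and grouping missing ALP with high ALP has no obvious rationale. This is a fair guide to the intention. It does not make the sentence say so, and an explanatory clause that contradicts the term it explains needs correcting.

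The second defence is that such a case would not go unseen. Section 9.2.1.4 requires permanent discontinuation for treatment-related, non-cholestatic cases. Section 7.2.5.1 counts any drug-related toxicity judged to require removal from the study. Section 9.2.7.1 makes these cases SAEs, AST/ALT more than 3-fold above baseline is an AESI, and the SMC confirms DLTs. These safeguards are real and cover much of the gap, but they do not close it. Stopping drug is not the same as removal from the study, 9.2.1.4 lets patients stay on treatment when benefit is judged to outweigh risk, and reporting an SAE or AESI does not make it a DLT.

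Third, the BOIN changes above are single-step actions, whereas the MTD is selected by isotonic regression (10.3.1). With one case added at 80 mg (2/5, 0/3, 0/9) or at 240 mg (1/5, 1/3, 0/9), patient-weighted pooling over the three doses gives 2/(5 + 3 + 9) = 2/17 = 0.118, well below 0.30. So the Part A conclusion at 800 mg survives one added case on the observed counts, although the escalation path might have differed.

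Finally, Part A is complete and the trial closed early, so new wording will guide few or no dosing decisions. That makes the data check the more useful half of the remedy, but the rule is still wrong as written.

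**Conclusion.** The concern holds. On its plain wording the Hy's Law arm is reversed; on the most generous reading it is ambiguous. The SAP inherits it rather than correcting it.

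The practical effect is small. It is confined to the two groups in step 3, part of which the other safeguards would catch. No misclassified patient is documented, and protocol 5.3.2 reports a single Grade 3 treatment-related transaminase event in Part A. Nothing here shows the 800 mg conclusion to be unsafe. The BOIN figures show only what one hypothetical missed case could do at each dose.

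The conclusion assumes that the inequality sign is printed in the signed protocol as it appears in the public text. That should be confirmed first.

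**What to change.** - In protocol 7.2.5.1, replace the end of the Hy's Law clause with: *with no evidence of hemolysis and with ALP <2 × ULN or not available*. This matches the cut-off in SAP 3.6.3 and counts a case when ALP was not measured. SAP 3.6.1 needs no edit because it refers to that section, and no wider harmonisation of signs or timing windows is needed.
- Query the liver laboratory listing for any case in the 28-day DLT period with AST/ALT above 3 × ULN and bilirubin above 2 × ULN, including those with missing ALP, among the up to 51 patients. Check each against the corrected rule and state the result in the study report. If there are none, one sentence settles it.

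The cost is one clause and one query. A protocol amendment that is not administrative also needs ethics committee approval (11.1). If the protocol is no longer being amended, stating the corrected rule in the study report with the result of the query would serve.

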DLTs must be confirmed by a SMC (consisting of study Investigators, Medical Monitor, and Sponsor observers) as related or relevant to treatment with NM21-1480. Patients with occurrence (with the exception of those listed above) of any Grade 3 or worse AE as defined above should be permanently discontinued from the study. All AEs (with the exception of those listed above) of the specified grades should count as DLTs except those that are clearly and incontrovertibly due to disease progression or extraneous causes.

A DLT will be considered related to study drug unless there is a clear, well-documented, alternative explanation for the toxicity.

All AEs that meet DLT criteria, as well as any Grade 3 or 4 infusion reactions whether or not the event is a DLT, must be reported as AESI within 24 hours using rapid notification procedures.

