8.1.5.1 Dose Reduction

In Part A, dose may be reduced to the next lower pre-specified dose level of the BOIN design due to toxicity if deemed necessary by the Investigator after consultation with the Medical Monitor, specifically after occurrence of a DLT.

Only one dose reduction is allowed.

In general, tolerability issues in both Part A and Part B are to be addressed by dose withholding; however, dose reduction may be considered upon discussion with the Medical Monitor if deemed necessary as per the Investigator's assessment.

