 1. Dosing delays to allow for prolonged steroid tapers to manage TRAEs may be allowed if approved by the Medical Monitor. Prior to re-initiating treatment in a patient with a dosing delay lasting >35 days (i.e., 2 missed doses + 7 days in settings with intended biweekly dosing events) or >49 days (i.e., 2 missed doses + 7 days in settings with intended dosing events every three weeks) from the scheduled dosing, the Medical Monitor must be consulted. Tumor assessments should continue as per-protocol even if dosing is delayed. Periodic study visits to assess safety and laboratory studies should also continue every 2 weeks or more frequently if clinically indicated during such dosing delays.
 2. Dosing delays lasting >35 days (i.e., 2 missed doses + 7 days in settings with intended biweekly dosing events) or >49 days (i.e., 2 missed doses + 7 days in settings with intended dosing events every three weeks) from the scheduled dosing that occur for non-drug-related reasons may be allowed if approved by the Medical Monitor. Prior to re-initiating treatment in a patient with a dosing delay lasting 35 days (i.e., 2 missed doses + 7 days in settings with intended biweekly dosing events) or 49 days (i.e., 2 missed doses + 7 days in settings with intended dosing events every three weeks), the Medical Monitor must be consulted. Tumor assessments should continue as per-protocol even if dosing is delayed. Periodic study visits to assess safety and laboratory studies should also continue every 2 weeks or more frequently if clinically indicated during such dosing delays.

Patients who meet toxicity related discontinuation criteria discussed above or presented in [Appendix VI](#), (management of irAEs) may be permitted to remain on therapy if the benefits are

considered to outweigh the risks of continued treatment after discussion between the Sponsor and Investigator and between the Investigator and the patient.

In case of development of a \geq Grade 3 (CTCAE V5.0) intolerance or AE related to NM21-1480 that precludes further treatment with the study drug, but patient does not have worsening progression: Patients will complete the remaining visits of their current treatment cycle (without infusions) if possible. Patients will then enter the Follow-up period.

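### Protocol section 7.2.5.1 lets dosing resume after a dose-limiting toxicity and, further down, calls for permanent discontinuation after nearly all of the same events

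*Protocol*

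**What the plan says.** Section 7.2.5.1 of the protocol defines DLTs over the first 28 days. It then states, in this order:

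- "Resumption of NM21-1480 administration for patients experiencing DLTs may be permitted", on three conditions: recovery to Grade 0-1 or baseline; "interruption or delay of treatment for no more than 35 days (i.e., 2 missed doses + 7 days) from the scheduled dosing"; and approval by the Medical Monitor.
- "The following events shall not be regarded as a DLT", which heads a list of nine kinds of event.
- After a paragraph on transaminase elevations, that patients with "any Grade 3 or worse AE as defined above should be permanently discontinued from the study", apart from the listed events.
- "All AEs (with the exception of those listed above) of the specified grades should count as DLTs", unless clearly caused by progression or something extraneous.

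Other sections also bear on dosing after toxicity:

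- **8.1.5.1** allows a step down to the next lower dose level in Part A, "specifically after occurrence of a DLT".
- **8.1.6** allows resumption once treatment-related events have settled to Grade 1 or baseline within the permitted delay.
- **9.2.1.4** requires permanent discontinuation for Grade 3 treatment-related non-skin events if they last more than 7 days, with exceptions, and for any Grade 4 toxicity. It adds that patients who meet its criteria, or those of Appendix VI, "may be permitted to remain on therapy" after a benefit-risk discussion.
- **Appendix VI** withholds the drug, rather than stopping it, for some Grade 3 immune-related events, such as a first Grade 3 diarrhea and Grade 3 dermatitis.

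**The concern.** When a Grade 3 DLT has settled, one section of the protocol supports both re-dosing the patient and never dosing again. The choice then falls to whichever paragraph the site reads. In a first-in-human trial this is a patient-safety instruction, so it should not be ambiguous.

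There is a smaller data consequence. Exposure after a DLT, and the later safety data that come with it, would depend on local reading. Best overall response (BOR) uses only scans taken up to 30 days after the last dose (protocol 10.6.2.2, SAP 3.4.1.1), so the dosing decision also affects which scans count.

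The later sentence also speaks of leaving the study rather than stopping the drug. SAP 3.3.1 tabulates these two outcomes separately, so the term needs a fixed meaning.

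**Working it through.** The plan gives no figure to reproduce beyond the delay limit, which is consistent: 2 missed doses × 14 days + 7 = 35 days. The check is a comparison of the texts.

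**1. Do the two rules cover the same patients?** Most DLT criteria in 7.2.5.1 are set at Grade 3 or above. The any-grade criterion applies only when the toxicity already requires removal from the study, so resumption does not arise. A few criteria carry no printed grade: death, febrile neutropenia, the Hy's Law combination and the enzyme thresholds for patients with liver metastases. The Hy's Law combination is offered as an alternative to Grade 3 transaminase elevation, so it may sit below Grade 3. The overlap is therefore large but not complete.

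**2. Does the exception separate them?** The discontinuation sentence exempts events listed above it. The only list of excepted events is the list of non-DLTs, and the next sentence uses the same exemption to define what counts as a DLT. It therefore protects events that are not DLTs and no event that is one.

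**3. A worked case.** Take treatment-related Grade 3 diarrhea lasting 4 days despite maximal treatment.

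| Place | Outcome |
|---|---|
| 7.2.5.1, definition | DLT: 4 × 24 = 96 hours, above the 72-hour limit; not in the non-DLT list |
| 7.2.5.1, resumption paragraph | May resume, on conditions |
| 7.2.5.1, later paragraph | Should stop permanently |
| 8.1.5.1 (Part A) | Dose may be reduced |
| 9.2.1.4 | The Grade 3 non-skin duration rule is not met: 4 days is below 7 |
| Appendix VI, if managed as immune-related colitis | Withhold; stop only if recurrent or Grade 4 |

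The later paragraph of 7.2.5.1 stands alone against the others.

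**4. Where the conflict has no practical effect.** It makes no difference for deaths, for DLTs that do not recover within 35 days, or for any-grade toxicities that require removal. Grade 4 events are stopped under 9.2.1.4 as well, subject to its benefit-risk provision. What remains is DLTs, mostly Grade 3, that recover in time.

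**5. How many patients.** Table 10-5 gives 1 + 1 + 3 + 3 + 5 + 3 + 9 = 25 evaluable Part A patients with one DLT, or 1/25 = 4%. SAP section 6 gives 5 patients in Part A-2 and 5 + 5 + 10 = 20 in Part B. The documents give no DLT count for these 25. For scale only, assume a rate between the 4% seen in Part A and the 30% used as the toxicity limit. That gives 25 × 0.04 = 1 to 25 × 0.30 = 7.5 patients with a DLT, of whom only some would recover in time.

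**6. Effect on BOR.** If dosing stops after Day 1 alone, the 30-day window closes on Day 31. The first scan in Parts A-2 and B falls on Days 39-43 (Table 7-1), so it would not count. If dosing resumes, the last dose moves later and that scan can count. If the last dose is on Day 15, the window runs to Day 45 and the scan counts either way.

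**The case against.** The best defence is that the text is permissive. Discontinuation is something that should happen and resumption something that may be permitted, so one could read a default with an exception granted by the Medical Monitor. That may be the intention. But the later sentence says permanently, names its own exception and does not mention resumption, so the reader has to supply the link.

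The benefit-risk provision in 9.2.1.4 does not supply it either. It refers to the criteria of its own section and Appendix VI, and it runs through discussion between Sponsor, Investigator and patient rather than Medical Monitor approval.

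Several points on the other side do stand:

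- **Not four rival outcomes.** Dose reduction under 8.1.5.1 is one way of resuming, and the 9.2.1.4 provision is an exception to a discontinuation rule. The direct contradiction lies within 7.2.5.1.
- **No loss of follow-up.** A reader might infer that leaving the study ends PFS and OS follow-up and so creates informative dropout, especially as SAP Table 1 censors PFS at study withdrawal. The documents do not support this. Section 9.2.1.4 sends patients with a related Grade 3 or worse event that precludes treatment, without progression, into the Follow-up period. Sections 7.2.9 and 7.2.12 and Table 7-1 footnote b require survival follow-up of all patients. Section 8.1.3 continues imaging until progression, and 9.2.2 and footnote z keep safety monitoring for 70 days. Section 7.2.9 expects patients who stop treatment to stay in the study. Appendix VI prints discontinuation from the study under its dose-modification column, which shows that the phrase is used loosely for stopping the drug.
- **Limited reach.** Part A patients had all finished treatment by November 2022 (5.1.3), so the 8.1.5.1 clause no longer affected anyone still on treatment.

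**Conclusion.** The point holds as an internal contradiction in 7.2.5.1. For a DLT, mostly Grade 3, that recovers to Grade 0-1 or baseline within 35 days, the section both permits resumption with approval and calls for permanent discontinuation. No other section resolves this, and 8.1.5.1, 9.2.1.4 and Appendix VI do not match the blanket sentence.

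The number of patients is small and not known exactly, because DLT counts for Parts A-2 and B are not in the documents. The conclusion assumes that the exempted events are the nine listed non-DLTs, the only list of excepted events in the section.

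Two wider readings should not be drawn. Not every patient with a DLT is affected, because several kinds of DLT lead to no resumption under either paragraph. DLT counting under the BOIN design is also untouched, because an event is counted whatever happens to dosing afterwards. The point deserves correction because it governs re-exposure after toxicity. This review takes no view on which rule is right.

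**What to change.** Reconcile 7.2.5.1 with 8.1.5.1, 8.1.6, 9.2.1.4 and Appendix VI so that one rule governs dosing after a DLT and the other sections refer to it. The sponsor and the Safety Monitoring Committee decide what that rule is.

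In the same edit:

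- State whether discontinuation in 7.2.5.1 means study drug or study participation, in line with 7.2.9 and 9.2.1.4, and use the same term in Appendix VI.
- Align the delay limit. Section 7.2.5.1 gives only the two-week figure, while 8.1.6 also gives 2 × 21 + 7 = 49 days for three-weekly dosing.

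The cost is wording only: the design, the sample size and the BOIN decision table do not change. Since the SAP describes early closure, the clinical study report should also record, for each patient with a DLT, whether dosing was resumed, reduced or stopped, and how that patient's BOR and PFS were derived.
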